Project Description

Date: 04/07/2022 Revision of Original Protocol to Adjust for Covid Pandemic

Project Title: Feasibility and Acceptability of The Equus Effect: A Small Randomized Controlled Pilot Study of an Equine-facilitated Therapy

Principal Investigator: [name].

Purpose

We propose to pilot test an innovative equine-facilitated therapy called The Equus Effect (TEE) as a complement to Veterans' existing VA mental health services to improve social functioning. TEE aims to improve Veterans' social functioning by developing their emotion regulation and interpersonal skills through therapeutic interactions with horses. In line with recommendations for pilot investigations, we will conduct a randomized pilot study to 1) evaluate the feasibility of study procedures, assessments, and outcomes, 2) demonstrate experimental and control interventions can be delivered with fidelity, and 3) examine the acceptability of the interventions. To accomplish these goals, we will enroll a transdiagnostic cohort of 40 Veterans involved in VA mental health services with social dysfunction and emotion dysregulation. We will randomize participants to receive either 1) TEE or 2) attention control (AC), both group interventions. Each week, the 4-session TEE will include 1) mindfulness activities, 2) emotion regulation and interpersonal skills education, 3) experiential activities with horses incorporating opportunities to develop emotion regulation and interpersonal skills, and 4) between-session application of lessons learned from the equine activities. AC will have similar elements without equine features. Intervention outcomes will be measured at 4- and 16-weeks post randomization. Specifically, using mixed quantitative-qualitative methods, we aim to:

Aim 1: Determine the feasibility of recruitment, randomization, retention, assessment procedures, and implementation of TEE and AC. *Hypothesis:* Rates of recruitment will be ≥ 8 participants per month, and Veterans randomized to TEE will attend intervention sessions, remain in the study, and experience clinically significant changes in social functioning and emotion dysregulation at rates equal to or superior to AC.

Aim 2: Demonstrate TEE and AC can be delivered with fidelity. *Hypothesis:* Facilitators will deliver each intervention consistently and as intended across sessions.

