Aim 3: Establish acceptability of TEE and AC by assessing intervention credibility and satisfaction and the usefulness of TEE as a complementary mental health intervention using mixed quantitative-qualitative methods. *Hypothesis:* Veterans will find TEE and AC credible and satisfying and Veterans and their mental health clinicians will qualitatively report the therapeutic benefits of TEE as a complementary and integrative health (CIH) intervention for mental health treatment.

This small pilot project takes a bold step forward in proposing to investigate EFT with scientific integrity and has the potential to lend initial credibility to the therapeutic claims of this increasingly popular CIH. Should data indicate that TEE and methods to study its effects are feasible and acceptable, it will set the stage for a RR&D IIR proposal to test the efficacy of TEE in a multi-site randomized controlled trial.

Background

In 2016 the VA Office of Patient Centered Care and Cultural Transformation (OPCC&CT) launched the Whole Health initiative to change VA's healthcare system from a traditional medical model focused on treating specific conditions to a more holistic personalized, proactive, patient-driven approach.¹ With Whole Health, Veterans develop healthcare plans that center on achieving meaningful life goals and improving functioning, consistent with a psychosocial rehabilitation emphasis on recovery-oriented outcomes related to functioning in the community.² A key component of Whole Health is the use of complementary and integrative health (CIH) approaches with traditional services. Currently, one facility in each of 18 VISNs are designated as VA Whole Health flagship sites, and many more VA facilities within each of these VISNs are implementing elements of the Whole Health system and expanding CIH options for Veterans.¹

One class of CIH is animal-facilitated therapy, such as the use of support dogs³ or interacting with horses.^{4,5} Among animals, horses confer unique therapeutic benefits. As prey animals, they are extremely sensitive to the environment and have developed an ability to assess the emotional states, behaviors, and intentions of their herds, other animals, and predators,^{6,7} mirror body language,⁸ and immediately respond to

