Justification. Veterans must report a moderate level of impaired social functioning (primary outcome) for study interventions to demonstrate clinically significant changes in this area; proposed cut-offs exclude Veterans who report few or no problems with social functioning. We also included a cut-off of at least moderate emotion dysregulation (secondary outcome) given how TEE and most EFTs purport to lessen emotion

dysregulation as a key mechanism to improve social functioning. Veterans must receive consistent mental health treatment from a clinician to enable qualitative examination of EFT's complementary therapeutic value. Phone contact is necessary to coordinate transportation to Sharon, CT and arrange study assessments.

5. Randomization. Eligible Veterans will be recruited to form one TEE and one AC group every four weeks. We will use permuted block randomization (1:1 ratio), with variable block size, to maintain balanced assignment to conditions given potential differences in monthly recruitment. The project coordinator will conduct randomization.

6. Recruitment and feasibility. Recruitment will begin at the end of Q2 in Year 1. In FY2018, VACHS served over 58,687 unique Veterans in Connecticut and southern New England, with 14,687 enrolled in mental health services. Most Veterans are seen at our West Haven and Newington campuses. The West Haven campus has five outpatient mental health clinics, three intensive outpatient treatment programs, two residential psychosocial rehabilitation treatment programs, and the psychosocial rehabilitation Errera Community Care Center. The Newington campus has two outpatient programs and two intensive outpatient treatment programs. We will recruit 8-12 Veterans per 4-week cycle to form a large enough cohort each month for block randomizing a sufficient number of Veterans to either TEE or AC. Hence, recruiting 40 Veterans should take about 4 months; we have planned seven months in our timeline in case recruitment is slower than expected. Recruiting 40 Veterans should be quite feasible given the large number of Veterans in VACHS mental health services, the broad transdiagnostic eligibility criteria, and record of Veteran engagement in TEE thus far (> 200 in the past 4 years).

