If VA DocuSign is infeasible to use with potential participants, the consent form will be mailed to subjects after participating in the phone screening to determine initial eligibility. Upon receipt of the consent form, another remote encounter will occur with the potential participant to review it, and have it signed and returned to the research team, if the Veteran remains interested. Once received, a member of the research team will meet remotely again with the participant to complete the screening, determine eligibility, and, if found eligible, have the participant finish the remaining baseline assessments. Remote sessions will not be recorded.

8. Intervention conditions. Veterans will receive either TEE or AC, both closed group programs in which all members begin the group intervention at the same time. TEE and AC each will consist of four 4-hour weekly sessions over 4-weeks, with 4-6 Veterans attending per 4-week cycle. Activities in both conditions contain a mixture of indoor and outdoor activities; group facilitators and participants will wear 2-ply face masks indoors or outdoors as dictated by prevailing VACHS guidelines. Masks will be provided to participants who do not have them. [name] and [name], LCSW will conduct TEE sessions. They are Experiential Learning with Horses Instructors who trained at the Epona Equestrian Services Program in Tucson, AZ – an internationally acclaimed equine educational program that trains people in EFT. They have worked together for the past decade developing and delivering TEE to Veterans. Peer specialists from VACHS or staff from the facility in Sharon, CT not delivering TEE will conduct AC sessions. They have experience facilitating general support groups and will be trained by [name] to deliver the control intervention.

TEE. Each session includes: 1) mindfulness-based activities; 2) didactics about emotion regulation and interpersonal skills; and 3) experiential learning activities with horses that provide opportunities to practice emotion regulation and interpersonal skills. At the end of each session, Veterans debrief about what they learned and identify how they might apply this knowledge to manage their mental health concerns and function better socially. [name] and [name] have prepared a manual detailing the program’s major components and content and will co-facilitate its delivery to participants in this pilot study.

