Key informant interviews. Key informant individual 20/30-minute interviews will take place post-intervention to assess Veteran and clinician perceptions of the acceptability, usefulness, and satisfaction of TEE. Drs. [name], [name], and [name], and [name] and [name] will develop the Veteran and clinician interview guides to ensure questions and probes ascertain main topics. These interviews will be audio recorded using either Microsoft TEAMS (from a VA desktop or laptop) or a VA-approved audio recorder. Microsoft TEAMS is a HIPAA-compliant, VA approved platform for video conferencing and has transcription generating capacity. We will also gather some demographic and professional characteristics of clinician participants (i.e., age, sex, race/ethnicity, profession/discipline, professional status (e.g., staff, trainee), Veteran status, months treating Veteran, years providing clinical services, and major focus of mental health service provided to Veteran) to characterize the sample.

10. Data management. Quantitative assessment measure responses will be entered into VA REDCap to provide secure automated export procedures for data to be downloaded to Excel and common statistical packages (e.g., SAS) for data analysis. REDCap catches unclear characters, out-of-range variable and logical inconsistencies. The research assistant will check files monthly so that errors can be readily corrected.

11. Data analysis.

Quantitative. To assess feasibility (Aim 1), we will use CONSORT reporting standards to diagram the number of Veterans screened, found eligible and ineligible (with reasons), consented, attended sessions, completed TEE and AC interventions, and retained through follow-up. We also will track rates of unanticipated study-related adverse events in both conditions and participants' rate of completion of all outcome measures. Means, standard deviations, and median scores will be calculated for outcome assessments. The proportions of participants with clinically significant change in outcomes from baseline to 4- and 16-weeks post-randomization will be calculated using each measure's test-retest reliability and clinical cutoffs from the literature, or change of two standard deviations from the baseline mean when clinical cut-offs are not available.⁴⁵ To assess intervention fidelity (Aim 2), we will determine the proportion of sessions that contain all

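### Aim 1 sets no absolute standard for attendance or retention; matching or exceeding AC is about as likely when both arms do badly as when both do well

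*Combined protocol and SAP*

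**What the plan says.** Aim 1 (Purpose) is about whether recruitment, retention, assessment and delivery of both interventions are workable. Its hypothesis has two parts. Recruitment has an absolute target: "Rates of recruitment will be ≥ 8 participants per month". The remainder is relative. It predicts that "Veterans randomized to TEE will attend intervention sessions, remain in the study, and experience clinically significant changes", and the sentence closes with the comparator: "in social functioning and emotion dysregulation at rates equal to or superior to AC".

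Research Plan section 11 (Data analysis, Quantitative) assesses Aim 1 with a CONSORT diagram that includes the numbers who "attended sessions, completed TEE and AC interventions, and retained through follow-up", together with completion of the outcome measures. It attaches no target to any of these. Section 6 (Recruitment and feasibility) has the study team review progress counts monthly, including withdrawals and completed assessments, and report them periodically to the DSMB, again without a target.

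The result has a stated use. The Purpose section says: "Should data indicate that TEE and methods to study its effects are feasible and acceptable", the pilot will lead to a proposal for a multi-site efficacy trial. It gives no numerical criterion for that step.

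**The concern.** Whether a randomized comparison of TEE with AC can be run depends on how many Veterans attend and stay in each arm. A comparison between arms answers a different question. It can be met when both arms lose half their Veterans, and for a given TEE rate it becomes easier to meet as AC does worse, although a trial that cannot keep its control arm is not feasible. It can also be missed by chance when both arms do very well. Since feasibility is the main purpose of this pilot, the team could report the Aim 1 hypothesis as supported, or not supported, for reasons that have little to do with feasibility.

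**Working it through.** The plan has no power, margin or sample-size figure to reproduce, so the check evaluates the stated criterion directly.

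**Inputs from the protocol**
- Total sample, from the Purpose section: "we will enroll a transdiagnostic cohort of 40 Veterans involved in VA mental health services".
- Allocation, from section 5: "We will use permuted block randomization (1:1 ratio), with variable block size". This gives 40 / 2 = about 20 per arm.
- Sessions and group size, from section 8: "four 4-hour weekly sessions over 4-weeks, with 4-6 Veterans attending per 4-week cycle".

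**Assumptions**
- True attendance and retention rates are not given; a range of 20% to 95% is used.
- Each outcome is treated as yes/no per Veteran, and the hypothesis as a comparison of observed proportions with no margin.

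**Step 1: the relative criterion with equal true rates.** Let X (TEE) and Y (AC) be independent Binomial(20, p). By symmetry,

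P(X ≥ Y) = ½ × [1 + P(X = Y)].

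The true rate p enters only through the chance of a tie, so the result must be nearly flat in p.

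| True rate in both arms | P(X = Y) | P(X ≥ Y) |
|---|---|---|
| 20% | 0.158 | 0.579 |
| 40% | 0.128 | 0.564 |
| 50% | 0.125 | 0.563 |
| 60% | 0.128 | 0.564 |
| 80% | 0.158 | 0.579 |
| 90% | 0.214 | 0.607 |
| 95% | 0.310 | 0.655 |

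The values at 20% and 80% are identical. If attendance and retention must both meet the criterion and are independent, the probability is 0.564² = 0.318 at 40% and 0.607² = 0.369 at 90%, which is equally uninformative.

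**Step 2: does the result depend on the simple model?**
- Counting person-sessions (20 × 4 = 80 per arm, treated as independent): 0.532 at 40%, 0.553 at 90%.
- Clustering in groups of 5 (beta-binomial simulation): 0.558 and 0.601 with an intraclass correlation of 0.05; 0.553 and 0.595 with 0.10.

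The pattern is the same in each case.

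**Step 3: what an absolute floor would do.** For illustration only, take at least 15 of 20 (75%). One arm meets it with probability P(X ≥ 15) = 0.0207 at a true rate of 50%, 0.8042 at 80% and 0.9887 at 90%.

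| True rate | One criterion, both arms | Two criteria, both arms, independent |
|---|---|---|
| 50% | 0.0207² = 0.0004 | below 0.0001 |
| 80% | 0.8042² = 0.647 | 0.8042⁴ = 0.418 |
| 90% | 0.9887² = 0.978 | 0.9887⁴ = 0.956 |

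A floor separates poor from good performance, which the relative criterion does not. The last column shows the price of requiring attendance and retention together. If the two outcomes coincided exactly, the joint probability would rise to the middle column, so at a true 80% it lies between 42% and 65% for positively related outcomes.

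**The case against.** **It is a hypothesis, not a decision rule.** This stands. Nothing in the protocol says that the larger trial follows if TEE matches AC, and the Purpose section leaves that step to an overall judgement that also draws on fidelity and acceptability. A reader might infer that the plan would issue a false go or no-go signal; the documents contain no such rule.

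**The absolute numbers will be seen.** This also stands. Sections 6 and 11 provide for counts of starters, completers, withdrawals and retained Veterans, so heavy attrition would be visible. A reader might infer that the pilot cannot show whether a trial is feasible; that goes too far. What is missing is a standard fixed in advance against which to read the counts.

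**The comparison with AC may apply only to clinically significant change.** The sentence can be read that way. The probabilities in Step 1 would then not describe attendance or retention, but those two outcomes would have no criterion at all, and the same remedy is needed.

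**Unequal rates might seem to make the case stronger.** TEE at 40% against AC at 30% meets the criterion with probability 0.798, while 85% against 95% meets it with probability 0.209. That contrast changes the direction of the arm difference as well as the level, so it does not isolate poor from good performance. The equal-rate figures are the relevant evidence.

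**Differential attrition is a proper feasibility question.** It is, and the comparison should be kept as description. It cannot replace a minimum level in each arm.

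**Conclusion.** The point holds as a defect in the prespecified success standard for attendance and retention. With equal true rates anywhere from 20% to 90%, the stated criterion is met 56% to 61% of the time, so meeting it is close to uninformative about the level in either arm. This rests on about 20 per arm, on assumed true rates and on a zero-margin comparison of observed proportions. It is not sensitive to counting sessions instead of Veterans or to moderate clustering within groups. Recruitment, which has its own number, is not affected, nor are the data to be collected. The change should be made, because feasibility is what this pilot sets out to establish.

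**What to change.** In the Aim 1 hypothesis, replace the comparison with AC, for attendance and retention, by minimum rates that apply to TEE and AC separately. Define each outcome per Veteran: how many of the four sessions count as adequate attendance, and at which assessment retention is judged. The sponsor should choose the figures and fix them before the monthly counts described in section 6 are reviewed; if some have already been seen, the protocol should say so. Report the TEE-AC difference in each rate with a confidence interval, as a description of differential attrition.

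Set the floors with the joint probability in view. The 75% floor above is only an example: applied to both outcomes in both arms, it could be missed more often than met at a true rate of 80% (about 42% met if independent), though it would be met about 96% of the time at 90%. Precision is also limited: 16 of 20 has an exact 95% interval of 56% to 94%.

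The cost is a change of wording, with no new data, since section 11 already includes these counts. The downside is that the pilot can now miss a standard that it would otherwise have met.

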The proposed pilot study will advance knowledge in rehabilitation research by studying the feasibility and acceptability of conducting a randomized controlled trial of an EFT, called The Equus Effect (TEE), currently available to Veterans at VA Connecticut Healthcare System (VACHS). TEE is a 4-session intervention that incorporates mindfulness strategies, emotion regulation and interpersonal skill development, and experiential equine activities to improve social functioning for a mixed diagnostic group of Veterans. Data from the pilot study will inform development of a RR&D IIR proposal testing the efficacy of TEE in a multi-site randomized controlled trial. The proposed research aligns with the RR&D SPiRE Program Priority Areas for studying

promising non-pharmacological activity-based interventions to maximize functional recovery,²⁵ OPCC&CT promotion of CIH within the Whole Health initiative,¹ and the VA 2018-2024 Strategic Plan to ensure Veterans receive integrated care and support that emphasizes their well-being and independence.²⁶

Research Plan

1. Study design and overview. We will test the feasibility and acceptability of a randomized controlled trial design to study TEE to improve social functioning. We will enroll a transdiagnostic cohort of 40 Veterans with social dysfunction and emotion dysregulation who are receiving VA mental health services and randomize them to either weekly TEE or attention control (AC) sessions over 4 weeks. Social functioning will serve as the primary outcome; emotion dysregulation will serve as the secondary outcome. Following best practice recommendations for pilot investigations,^{27,28} we will use mixed quantitative and qualitative methods. Feasibility will examine performance of study procedures, assessment measures, and outcomes (Aim 1) and fidelity of TEE and AC (Aim 2). Acceptability will involve assessing TEE and AC credibility and satisfaction, as well as conducting key informant interviews with Veterans assigned to TEE and their clinicians (n = 20) to examine perceptions of the acceptability and usefulness of TEE and the ways in which it complements standard mental health care (Aim 3). Intervention outcomes will be measured at baseline and 4- and 16-weeks post-randomization.

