2. Study timeline. Year 1 will include start-up tasks and initiating the pilot trial. Year 2 will involve completing the pilot trial, cleaning and analyzing data, and preparing manuscripts and the RR&D IIR RCT proposal to test TEE efficacy (see Table 1).

Table 1. Study Timeline.

Activities	Year 1				Year 2			
	Q1	Q2	Q3	Q4	Q1	Q2	Q3	Q4
IRB	X	X						
Hire and train RA	X	X						
Develop AC	X	X						
Develop TEE and AC fidelity measure		X	X					
Recruit participants/provide TEE & AC		X	X	X				
Complete assessments		X	X	X	X			
Enter and clean data		X	X	X	X	X		
Analyze data					X	X		
Present findings						X	X	
Prepare manuscript and RR&D IIR RCT						X	X	

3. Setting. All research procedures will be conducted at VA Connecticut West Haven and Newington campuses. TEE and AC will be delivered off-site at the TEE location in Sharon, CT.

4. Participant eligibility criteria. Inclusion criteria for Veterans are: 1) seeing a VACHS mental health clinician at least three times in the past 3 months with intent to remain in treatment during study enrollment; 2) age 18 and over; 3) social dysfunction (score \geq 2.5 on the Social Adjustment Scale—Self-Report or \geq 1.5 on the Inventory of Interpersonal Problems—32); 4) emotion dysregulation (score \geq 95 on Difficulties in Emotion Regulation Scale); and 5) consent to all study procedures, including audio recording of group intervention sessions. Exclusion criteria are: 1) psychotic disorder as self-reported by the Veteran and verified in the electronic health record or as determined by the Mini-International Neuropsychiatric Interview; 2) acute suicidality, 3) inability to read English or communicate in spoken English; 4) anticipated unavailability to the study during the next 16 weeks; 5) participation in any EFT in the past 24 weeks; and 6) unavailability of a landline or cellular telephone. Clinicians are eligible for study participation if 1) they have seen one of the Veteran participants assigned to TEE at least three times in the past 3 months at the participant's baseline assessment, and 2) this Veteran received at least one TEE session and one psychotherapy/counseling session with the clinician prior to the key informant interview.

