Direct-to-participant and clinician recruitment will occur via flyers, visits to clinic rounds, and email to clinicians at VA Connecticut sites, including Vet Centers in Connecticut. The study also will be presented to Veterans during community meetings at Errera Community Care Center programs located in West Haven and Newington. In addition, clinicians and peer specialists will be provided with study cards that they can hand to Veterans if they feel the Veterans might be appropriate for study participation. If Veteran participants have more than one mental health clinician, they will be asked to identify which clinician they see as primarily providing them mental health psychotherapy/counseling, and the research assistant will invite that person to participate in the study. The decision of Veterans' clinicians to enroll in the study will not affect potential Veteran participants' study eligibility, particularly because their clinicians will be approached for study participation after Veterans have already enrolled. The PI, project coordinator, and Co-Is will have monthly meetings to review the number of individuals assessed for eligibility and those who were found ineligible (with reasons), declined to participate (with reasons), randomized, started, completed, withdrew, and completed assessments at each timepoint. Quarterly/semi-annual reports of these numbers will be provided to the Data Safety Monitoring Board (DSMB).

7. Screening. We will seek waivers of written informed consent and HIPAA authorization for an initial phone screening. The research assistant (RA) will offer Veterans information about the study and invite interested parties to complete a brief phone screening on quickly obtained eligibility criteria (e.g., if they have received EFT in the past 6 months). Individuals who remain eligible will next attend an in-person meeting in which to learn more about the study in detail, including completing an additional screening to further determine inclusion and exclusion criteria (e.g., completion of psychiatric interview, social functioning, and emotion dysregulation assessments). If the potential participant is agreeable, the RA will invite individuals to provide written informed consent and then will complete the screening to determine eligibility. Only individuals who meet eligibility criteria will be invited to continue in the study and participate in the baseline assessment.

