Rationale for AC. For most Veterans, interacting with horses will be an unusual experience, and driving to the countryside and spending four hours in a bucolic setting may confer therapeutic benefits (e.g., stress reduction). Replicating TEE without horse-specific components will be essential to determine therapeutic gains specific to equine interactions. We elected not to include interactions with another large, familiar animal (e.g., a cow) as a more stringent test of “the equus effect” because of its impracticality, uncommonness as a

social/recreational activity, and the possibility that other animals could elicit different responses from different people (e.g., fear/hesitation vs. attraction/approach), making interpretation of potential condition differences difficult.

Table 2. TEE vs. AC.

		Content/Activities	
Session	Focus	TEE	AC (manual to be developed)
1	Mindfulness	Joint fluidity/body scan in horse barn	Joint fluidity/body scan in cottage
	Emotion regulation & interpersonal skills	Fear and vulnerability/video, discussion w/ parallels to horses	Fear and vulnerability; video, discussion; no horse parallels
	Experiential learning activity	Setting healthy boundaries/grooming, leading, yielding, backing up with horse	Team building activity requiring disclosure and boundary management
2	Mindfulness	Joint fluidity/body scan in horse barn	Joint fluidity/body scan in cottage
	Emotion regulation & interpersonal skills	Anger/Frustration/Agitation; video, discussion w/ parallels to horses	Anger/Frustration/Agitation; video, discussion; no horse parallels
	Experiential learning activity	Collaboration/ grooming, obstacle course with horse	Team building activity requiring collaboration
3	Mindfulness	Joint fluidity/body scan in horse barn	Joint fluidity/body scan in cottage
	Emotion regulation & interpersonal skills	Sadness and Grief; video, discussion w/ parallels to horses	Sadness and Grief; video, discussion; no horse parallels
	Experiential learning activity	Collaboration/ grooming, walk through labyrinth or trail with horse	Team building activity requiring collaboration
4	Mindfulness	Joint fluidity/body scan in horse barn	Joint fluidity/body scan in cottage
	Emotion regulation & interpersonal skills	Review of emotional states; video, discussion w/ parallels to horses	Review of emotional states; video, discussion; no horse parallels

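### Exclusion 5 lets earlier participants in The Equus Effect enter the trial, and the plan neither records nor analyses that exposure

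*Combined protocol and SAP*

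**What the plan says.** Section 4 lists one criterion on earlier EFT, exclusion 5: "participation in any EFT in the past 24 weeks". Section 7 gives, as an example of what the phone screen asks, "if they have received EFT in the past 6 months". No section bars Veterans who took TEE before that window.

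The Significance section presents TEE as an EFT that VA Connecticut already makes available. Section 6 supports recruitment feasibility by citing the "record of Veteran engagement in TEE thus far (> 200 in the past 4 years", alongside a pool "with 14,687 enrolled in mental health services".

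Entry requires current impairment: SAS-SR of at least 2.5 or IIP-32 of at least 1.5, plus a score of at least "95 on Difficulties in Emotion Regulation Scale".

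Section 8 defines AC as the same programme with all horse content removed, so that any benefit due to the horses can be isolated. Its rationale begins: "For most Veterans, interacting with horses will be an unusual experience".

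**The concern.** The treatment under test is already in use in the health system that supplies the participants, and the only protection against earlier exposure to it is a time window. Section 4 justifies several of its criteria but gives no reason why 24 weeks is long enough for a programme that teaches skills.

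A past TEE participant allocated to TEE repeats the programme. One allocated to AC has already had the component that AC is built to leave out. Three things are exposed:

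- the Aim 1 comparison of clinically significant change between arms;
- the Aim 3 credibility, satisfaction and interview data, which would combine first impressions with those of returning participants (one such Veteran in TEE can affect two interviews, the Veteran's and the clinician's);
- the use of both in planning the later efficacy trial.

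Because exposure is not recorded, the report could not show whether any of this had happened.

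**Working it through.** The plan gives no figure for earlier TEE exposure, so there is none to reproduce. The check is first of the text, then of the likely count.

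**Text**

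1. TEE within the past 24 weeks: excluded (section 4, exclusion 5).
2. TEE before that: no criterion applies. The Veteran is eligible if the other criteria are met.
3. Randomization: 1:1 permuted blocks, with no stratification factor named (section 5).
4. Sample description: demographics, military service and a psychiatric interview. None is designated for lifetime EFT or TEE (section 9).
5. Analysis: none by earlier exposure (section 11).

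**Count**

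Inputs from the protocol: 200 past participants in 4 years (section 6 says more than 200), a pool of 14,687 (section 6), a 24-week window (section 4), and 40 enrolled, so about 20 per arm (sections 1 and 5).

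Assumptions: the 200 are spread evenly over the 4 years, all are still in the pool and eligible, and each is as likely to be enrolled as anyone else in the pool.

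- Share inside the window: 24 / (4 × 52.18) = 24 / 208.7 = 11.5%.
- Past participants outside it: 200 × (1 − 0.115) = 177.
- Share of the pool: p = 177 / 14,687 = 1.2%.
- Expected among 40: 40 × 0.01205 = 0.48. Expected among 20 in AC: 0.24.
- P(at least one of 40) = 1 − (1 − 0.01205)^40 = 38%.
- P(at least one of 20 in AC) = 1 − (1 − 0.01205)^20 = 22%.

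If past participants are over-represented among volunteers, p is multiplied by a factor that the documents do not give. The factors of 5 and 10 below are assumptions chosen to show the range.

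| Factor (assumed) | p | Expected of 40 | Expected in AC | P(at least one in AC) |
|---|---|---|---|---|
| 1 | 1.2% | 0.48 | 0.24 | 22% |
| 5 | 6.0% | 2.4 | 1.2 | 71% |
| 10 | 12.1% | 4.8 | 2.4 | 92% |

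**Effect on the contrast**

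Suppose a share q of each arm has had TEE before and shows no TEE–AC difference. The observed contrast is then (1 − q) times the contrast in new participants. The loss is about 1%, 6% and 12% for the three rows. That is a deliberately unfavourable supposition, since past participants may still respond.

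**Chance imbalance**

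With 20 per arm and two past participants, both fall in the same arm with probability 2 × (20 × 19) / (40 × 39) = 49%. With four, a split of 3–1 or 4–0 has probability 60%. Each such Veteran is 1/20 = 5 percentage points of an arm's rate, but moves the rate only if that Veteran's outcome differs from what a new participant's would have been.

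**Window wording**

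24 weeks is 24 × 7 = 168 days; 6 months is about 365.25 / 2 = 183 days.

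**The case against.** This is a feasibility and acceptability pilot with a descriptive analysis and no powered test, so no error rate changes. That stands, and it limits the weight of the point. A time-limited washout is also a recognisable design choice. Further, the AC rationale speaks only of most Veterans, so it already accepts that some will have been around horses. Having met horses, however, is not the same as having taken the programme under test. On the random-draw figures there is about a 62% chance that no past participant enrols at all; that too stands, as far as those assumptions go.

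A reader might infer that past participants who qualify are TEE non-responders, so that the trial is loaded against TEE. The documents do not support this. The cut-offs measure current level, not change. On the DERS range of 36 to 180, a Veteran who went from 150 to 100 and stayed there would still meet the section 4 cut-off. Section 6 counts engagement, not completion, so dropouts are included. People who relapsed after a good response qualify too, and those who liked TEE may return and raise its credibility scores. Randomization also places past participants in both arms in expectation.

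A reader might likewise infer that lasting skills carry over into AC. No section shows that the effects last, and the Background says that EFT research has lacked post-intervention follow-up.

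**Conclusion.** The gap is real on the text: earlier recipients of the experimental treatment can be enrolled and cannot be identified in the results. They may be non-responders, partial responders, relapsers or dropouts. The harm is dilution, possible imbalance at about 20 per arm, and acceptability data of mixed origin. It is not a bias of known direction against either arm.

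The size is unknown. The 0.48 of 40 is not a bound in either direction. The 200 is a minimum for four years, and section 8 describes a decade of delivering TEE. On the other side, the protocol does not say that those Veterans were all patients in the 14,687 pool, and many may no longer qualify. A reader might expect several past participants among the 40. That needs over-representation among volunteers, which is plausible but has no figure in the documents.

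This is a cheap improvement to the interpretability of Aims 1 and 3, not a defect that invalidates the pilot.

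**What to change.** Add any prior participation in The Equus Effect to exclusion 5, keep the time window for other EFT, and ask about both at the phone screen. Record lifetime TEE and other EFT exposure at baseline.

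For Veterans already randomized, record lifetime exposure before randomization, report the count by arm, and show the Aim 1 change rates and the Aim 3 credibility and satisfaction scores with and without exposed Veterans. Exposure is a pre-randomization characteristic, so leaving those Veterans out of a sensitivity summary does not in itself undo the randomized comparison. The project coordinator, who carries out randomization, should collect it rather than the blinded research assistant, so that the question does not prompt disclosure of allocation. If the investigators prefer to keep the eligibility rule, the recording and the two-way reporting are the minimum.

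Cost: one eligibility sentence and one screening question. The pool shrinks by roughly 200 / 14,687 = 1.4%, or 177 / 14,687 = 1.2% beyond those the present window already excludes, on the assumptions above. Those lost may be among the keener volunteers.

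As an editorial matter only, sections 4 and 7 should state the same window.
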